### 3.0 Inclusion and exclusion criteria:

# We will recruit 180 IPS clients at Thresholds diagnosed with a mental disorder with or without psychotic features into the randomized controlled trial. *Inclusion/exclusion criteria are outlined below:*

Inclusion Criteria: 1) Over 18 years old;

2a) all chronic schizophrenia spectrum disorders, including schizophrenia, schizoaffective disorder, delusional disorder, brief psychotic disorder, schizophreniform disorder, other specified schizophrenia spectrum and related disorder, and unspecified schizophrenia spectrum and related disorders;

2b) all bipolar spectrum disorders beyond bipolar type I and II to include cyclothymia, other specified bipolar and related disorder, and unspecified bipolar and related disorders;

2c) all depressive disorders, including disruptive mood dysregulation disorder, major depressive disorder, persistent depressive disorder, other specified depressive disorder, and unspecified depressive disorder;2d) post traumatic stress disorder

3) fluency in English; 4) at least a 4th grade reading level; 5) enrolled in IPS; 6) active IPS enrollee as indicated by at least 1 contacts with his/her Employment Specialist in the past 30 days; 7) currently unemployed or underemployed; 8) Planning to go on interviews within 4 weeks of enrolling in the study; 9) willing to be video recorded; and 10) willing and able to provide informed consent. We will review each participant's medical record to confirm his/her mental health history.

Exclusion Criteria: 1) documented developmental or learning disability; 2) medical condition that may compromise cognition (e.g., Parkinson's Disease, Alzheimer's Disease, Huntington's Chorea, Moderate or Greater TBI); 3) uncorrected vision or hearing problems; 4) active suicidal ideation within the last 30 days with at least some intent to act, with or without a specific plan; this would be reflected in a score of 4 or 5 on the Suicidal Ideation section of the Columbia Suicide Severity Rating Scale (CSSRS); and 5) a past suicide attempt within the past 30 days that did not include preparatory acts or behavior, but was defined by a potentially self-injurious act committed with at least some wish to die as a result of the act.

We will not include any special populations: adults unable to consent; minors; infants; childrens; teenagers (ages 17 and younger); or prisoners.

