Data Analysis Plan for Aims 1 & 2. In this intent-to-treat study, we will collect data on 160 subjects. The biostatistician will monitor the data for distribution normality and transform abnormally distributed variables if needed. Correction for Multiple Comparisons: To minimize spurious findings, we will adjust the 3 primary tests using a false discovery rate at 0.05 (see below). Covariates: Although randomization should protect against group differences, we will covary for any between-group differences that are observed regarding demographic, cognitive, clinical and vocational history, booster sessions, and the number of completed interviews. Missing Data: We will follow the intent-to-treat principle and in longitudinal analyses we will use multiple imputation models to analyze the data in the presence of missing data. Data processing and cleaning will occur during the study, including checking for missing data and inconsistencies. All videos will be stored on the project's secure server. A Data Safety and Monitoring Board will monitor for adverse events (see 15.0 below).

**Hypothesis 1:** IPS+VR trainees will have higher employment rates than IPS Only by T3. **To test H1**, we will use multiple logistic regression and a Wald Chi-square test of the coefficient to its standard error, to compare the adjusted employment proportions in the two conditions (attained a job=1 vs. failed to attain a job or censored with a job=0, between T1 and T3). We calculated power using simulation in R, correcting for small samples and multiple testing with false discovery rate for the 4 primary tests (our power analysis is conservative, relying on Bonferroni corrections for all tests). Accounting for 10% missing, our trial that recruits 80 subjects in each arm has 80% power for a two-sided 0.05/4=.0125 level test when the OR = 3.2, with IPS+VR effectively doubling the

rate from 25% to 53% employment. Based on our earlier study where we found an OR of 8.7, or effectively tripling the employment rate from 25% to 75%, and a power of 0.99 at this magnitude of effect, we feel confident that we will have sufficient power in this study.

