**Hypothesis 2:** IPS+VR trainees will have greater improvement in *job interview skills* than IPS Only by T2. **To test H2**, we will conduct a repeated measures analysis of variance (RM-ANOVA) with pre and post interview scores as the repeated measures and treatment group as the fixed factor. Based on our pilot data, we expect r=.7 between T1 and T2 scores, and an effect size of d=.67 between pre and post interview role-play scores using VR. Assuming a small-to-moderate effect within IPS Only (e.g., d=.25), our best power estimate assumes a medium effect size contrasting IPS Only with IPS+VR (d=.67-.25=.42). This effect size and correlation imply an expected 6.9% reduction in within subject error for the treatment–x-time effect. Thus, 80 subjects at .0125 level will yield 82% power to detect this effect. For the ANOVA model, 160 subjects will be sufficient to detect a reduction of within subject error of 4.7% with 80% power. Assuming a full sample effect size of d=.46 (.67+.25)/2), this reduction in error corresponds to an effect size of d=.62 for the IPS+VR group and d=.30 in the IPS only group (a difference of d=.32).

**Hypothesis 3:** IPS+VR will get jobs sooner than IPS only by T3. **To test H3**, we will use a Cox proportional (or non-proportional) hazards regression model to assess the adjusted hazard rate on time-to-employment for IPS+VR vs. IPS Only, adjusting for potential covariates (e.g., completed training trials). For a power analysis for **H3**, we assume a constant hazard rate for the distribution of time-to-employment in both groups. We also assume that a proportion of 0.20 of the subjects in the IPS Only group will find a job by T3 (that is, a hazard rate of 0.0085 for IPS Only). This analysis is estimated based on limited pilot data and log-rank power tables. Thus, 160 subjects provide 80% power for a 0.0125-level test comparing time-to-employment in the two arms to detect a hazard rate of 2.0 for IPS+VR vs. IPS Only.

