**Hypothesis 6:** Improved interviewing skills will mediate the relationship between VR (number of completed VR trials and employment outcomes (obtaining employment). **To test H6**, we will test first for a significant IPS+VR impact on role-play scores compared to IPS alone, then check for treatment by mediator interaction, then on the product of the two coefficients with bootstrapped confidence intervals. We simulated power for this text, finding 80% power when the effect size for skills is small (effect size=0.2) and the odds for skills leading to a job is 1.8; thus we expect to have sufficient power. These older mediational models are informative but incomplete, and these will be followed by computing the *causally interpretable average natural indirect effect* under assumptions i – iv therein. We plan to conduct sensitivity analyses to the assumption of "no exposure induced mediation-outcome confounding". For the exploratory moderated mediation model, we plan to use Approach 1 of Vanderweele et al. to account for the combined mediated (indirect) effect of both the psychological changes in self-efficacy, anxiety, and role-play scores, as suggested in Corbiere et al..

**Exploratory:** To test the moderated mediation (mediated effect varies as a function of a baseline variable), we will first conduct a standard model of post-intervention anxiety/self-efficacy serving as a mediator of the relationship between VR and interviewing skills using the "product of coefficients method". Mediation tests will be based on whether the confidence interval for the product of coefficients includes zero. This approach addresses the known non-normality of the test statistic. To this standard mediation model we will include an interaction of baseline (pre-intervention) anxiety/self-efficacy to interact with VR training on post-intervention anxiety/self-efficacy. Similarly, we will include a baseline-by-intervention interaction on interviewing skills. The Johnson-Neyman approach will assess where mediation occurs as a function of baseline levels. We will test if employment outcomes mediate the relationship between interviewing skills and psychological distress at 6-month follow-up, using the same approach outlined for **H6**.

### Data Analysis Plan for Aim 3

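### The 80% power claimed for H6 at a small skills effect of 0.2 cannot be reached if 0.2 is Cohen's d; if 0.2 is on another scale, small is the wrong label

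*Combined protocol and SAP*

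**What the plan says.** Section 14.0, Data Analysis Plan for Aims 1 & 2, Hypothesis 6, sets out a sequence. For the first step, "we will test first for a significant IPS+VR impact on role-play scores compared to IPS alone". A check for treatment-by-mediator interaction follows, then the product of the two path coefficients with a bootstrapped interval. The power statement is one clause: "finding 80% power when the effect size for skills is small (effect size=0.2) and the odds for skills leading to a job is 1.8". From it the plan expects sufficient power. The clause gives no metric for 0.2, no alpha, no sample size, no unit for the odds, no job rate and no model.

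Hypothesis 2 in the same section concerns the same role-play scores and works in d. It says "our best power estimate assumes a medium effect size contrasting IPS Only with IPS+VR (d=.67-.25=.42", with a pre-post correlation of .7. It then says "160 subjects will be sufficient to detect a reduction of within subject error of 4.7% with 80% power", and equates that reduction with d=.62 against d=.30, a difference of .32. Hypothesis 4 also uses d.

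On sample size, Hypothesis 1 says "Accounting for 10% missing, our trial that recruits 80 subjects in each arm has 80% power", while Section 3.0 says "We will recruit 180 IPS clients at Thresholds".

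**The concern.** A mediation test that begins with a significant arm effect on the mediator cannot have more power than that first step. Detecting d=0.2 between two arms of about 80 is a hard task, and 80% power for a test that contains it looks impossible. The effect sizes in the neighbouring hypotheses are in d, and 0.2 called small is the usual d convention, so a reader will take the sentence that way.

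H6 is the only stated hypothesis of Aim 2; the others under that aim are exploratory. If H6 is null, a reader who relies on this sentence could conclude that even a small mediated effect has been ruled out, when the test had little chance of finding one.

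**Working it through.** **Inputs.** From the plan: 80 per arm; 72 per arm after 10% missing (80 × 0.9); 90 per arm if 180 are recruited (180/2); r=.7 between pre and post scores. Assumed, because H6 does not state them: two-sided 0.05, odds ratio 1.8 per SD of skills, 25% control job rate, no direct effect of arm on employment.

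**1. Reproduce H2, to fix a method.** For change scores, f = d / (2√(2(1−r))), and the proportional reduction in within-subject error is f²/(1+f²). At d=.42, f = .42/(2 × .7746) = .271, f² = .0735, and the reduction is .0735/1.0735 = 6.85% (stated 6.9%). Power at the .0125 level with 80 per arm is .815 (stated 82%). The method matches the plan's.

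**2. Power of H6's first step if 0.2 is d.** Two-sample noncentral t with noncentrality (d/s)√(n/2), where s = 1 for post scores, √(2(1−.7)) = .775 for change scores and √(1−.49) = .714 for ANCOVA. With n = 80, √(80/2) = 6.325 and the noncentralities are 1.265, 1.633 and 1.771.

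| n per arm | Post score | Change score | ANCOVA |
|---|---|---|---|
| 72 | 22% | 34% | 39% |
| 80 | 24% | 37% | 42% |
| 90 | 27% | 41% | 46% |

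A one-sided 0.05 ANCOVA gives only 55% at 80 per arm and 59% at 90. Reaching 80% for this step at d=0.2 would take 394, 237 or 202 per arm. None of this uses the odds ratio or the job rate.

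**3. Compare with H2's 4.7% statement.** Inverting the formula, f² = .047/.953 = .0493, f = .222, and d = .222 × 2 × .7746 = .344. The power at that d is .797 at 0.05 but .612 at .0125, so the stated 80% implies alpha 0.05. The plan itself equates 4.7% with d=.32, which is 4.1% on the change-score scale and 4.8% on the ANCOVA scale. The pair is therefore not exactly consistent. Either value is well above 0.2, which is a 1.6% reduction (f² = .0167).

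**4. Full H6 test by simulation.** Success means that step 1 is significant and the interval for the product excludes zero (Monte Carlo interval, 9,000 trials per case).

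| d, n per arm | No baseline | Change score | Baseline in skills model | Baseline in both models |
|---|---|---|---|---|
| .20, 72 | 16% | 25% | 28% | 17% |
| .20, 80 | 19% | 30% | 34% | 21% |
| .20, 90 | 22% | 35% | 39% | 25% |
| .40, 72 | 53% | 71% | 75% | 48% |
| .40, 80 | 59% | 77% | 80% | 55% |
| .40, 90 | 67% | 84% | 87% | 62% |
| .42, 72 | 57% | 74% | 78% | 51% |
| .42, 80 | 64% | 80% | 83% | 56% |
| .42, 90 | 70% | 86% | 88% | 63% |

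At d=0.2 and 80 per arm, control job rates of 20% to 40% give 17% to 37%. Judging by joint significance or a percentile bootstrap instead gives 20% to 39% at d=0.2. At d=0.4, joint significance gives 81% to 84% with change scores or baseline-adjusted skills.

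**5. Other metrics.** If 0.2 is Cohen's f, d = 2 × 0.2 = 0.40. If it is a correlation, d = 2 × 0.2/√(1−0.04) = 0.41. Step 4 then gives roughly the stated 80% in the two middle columns, and about 55% to 64% in the outer columns at d=.40 to .42 with 80 per arm.

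**The case against.** The strongest reply is that the sentence says effect size, not d, although H2 and H4 write d throughout. H6 also describes the exposure as a count of completed VR trials, for which a correlation or standardized path is a natural metric. On that reading the simulation may be right. This stands: a reader might infer that the simulation was wrong, and the documents do not show that. It does not rescue the sentence, because d of about 0.4 is essentially the .42 that H2 labels medium.

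It is also fair to say that the H2 cross-check is imperfect. Its 4.7% and d=.32 do not match on the change-score scale, and the stated power needs alpha 0.05 although the sentence before it uses .0125. It is therefore supporting evidence only. The first-step calculation does not depend on it.

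The effect size at which H6 reaches 80% depends on the model and criterion. It is near d=.37 to .42 with change scores or baseline-adjusted skills and near .5 with no baseline. With baseline in both models it is not reached by .5, and a one-sided ANCOVA reaches it near .3. No single threshold should be read as exact.

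Finally, the practical harm is limited. H6 lies outside the hypotheses for which the plan sets the .0125 level (H1 to H4), and it will be reported with an interval and followed by causal mediation and sensitivity analyses. That moderates the importance but leaves the sentence uncorrected.

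**Conclusion.** The sentence is wrong as written on each of the readings considered. If 0.2 is d, 80% power is out of reach: the first step caps it at 24% to 42% with 80 per arm, and at 27% to 46% with 90, at two-sided 0.05. The full test has roughly 20% to 40%. If 0.2 is f or a correlation, the power is about right for models that gain from the baseline score, and the word small is wrong.

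The cap rests on the plan's r=.7 and the assumed alpha. The full-test figures also rest on an odds ratio per SD, a 25% control job rate and no direct effect, none of which H6 states.

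A reader might go further and infer that H6 is underpowered for the effect the trial expects. The documents do not support that in general. At the planned d=.42 with 80 analysed per arm, change scores or baseline-adjusted skills give about 80% to 83%. That falls to 74% to 78% at 72 per arm, and to 56% to 64% at 80 per arm with no baseline or with baseline in both models. What fails is the claimed sensitivity to a small effect.

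**What to change.** Re-run the H6 simulation and restate the sentence with the metric of 0.2, alpha and sidedness, N after missing data, the unit of the 1.8 odds, the control job rate, and the model, including where the baseline score enters. Then either describe the detectable effect as about d=0.4 (medium) under that model, or report the much lower power at d=0.2. The figures should come from the sponsor's own re-run, since those given here rest on assumptions that the plan does not state.

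Drop the claim of sufficient power for a small effect. It may stand for the planned d=.42 with 80 analysed per arm and change scores or baseline-adjusted skills.

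The cost is one re-run and a change of wording. The design, the sample and the H6 test stay as they are. The downside is that the stated sensitivity becomes less favourable.

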#### Study Procedures, Measures, and Data Analysis

The mixed-method process evaluation will entail conducting focus groups and semi-structured interviews:

• Focus groups will be conducted with clients to assess: barriers (e.g., using computers) and facilitators (e.g., accessibility) to the implementation (i.e., delivery) of VR. The focus group with clients will assess perceptions of initial VR implementation, with results guiding immediate modifications to VR delivery. The focus groups with Team Leaders and Employment Specialists will assess perceptions of changes made to VR delivery and elicit new barriers/facilitators (e.g., changes in VR accessibility), with results guiding new modifications to VR delivery. We will track which subjects receive a modified delivery of VR, to be evaluated as a possible covariate. In total, 2-4 video-recorded focus groups (60 minutes, 4-6 participants each) will be conducted until reaching saturation (i.e., no new topics emerge).

• Qualitative Analysis: transcribe focus group data, analyze data iteratively using thematic analysis and the constant comparative approach to identify emergent themes regarding the barriers and facilitators of implementing VR. Two research staff will analyze the data using The Ethnograph, a qualitative data analysis package. Staff will independently analyze a subset of transcripts to iteratively develop codes inductively as they emerge, and deductively based on initial topics (e.g., barriers, available resources). After the team agrees on a final codebook and inter-coder reliability is achieved, the codes will be applied to all transcripts. We will use framework analysis to compare client, staff, and leaders' perceptions of barriers and facilitators to VR implementation. To facilitate comparison, a matrix of themes will be developed: subject type (x-axis) vs. barriers and facilitators (y-axis). Matrices will identify y-axis themes common to all groups, and features specific to particular subgroups. For instance, the experience of implementing VR for clients may be related to organizational themes not evident among staff or leaders.

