The Thresholds Research Coordinator will schedule the study participants to complete 6 two-hour sessions of VR. When participants show up for the VR training, the visit will be run the Thresholds research staff who will provide the trainee with an initial orientation to VR and then monitor the trainee's access and performance scores during the sessions. After completing the initial 6 visits, trainees will move on to complete their post-test visit. Trainees will be invited to use VR as-needed after completing the post-test visit, which will be monitored by the Team Leaders. Those participants assigned to the SE as usual group will have the option to use the VR training in the context of their regular use of Thresholds services (i.e., they will not have access to the study resources to use VR) following the completion of their participation in the study (after their 9-month follow-up phone call). At each training session, any subject who has had to travel to use the intervention will receive \$10 to reimburse them for the cost of transportation.

A note on VR delivery procedures (1/29/18): When the study initially began, Employment Specialists and Team Leaders were asked to run the VR orientation and training sessions. Due to workload expectations and coordination barriers, this responsibility was moved to the Thresholds Research Team.

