For the Thresholds clients who do not find employment during before this time, participation is complete for this study after finishing their 9-Month Follow-Up Telephone Call.

**E. 1. Level 1.** The first level for the process evaluation of VR includes two pre-study implementation evaluations. The first is a 12-item Implementation Leadership Scale (<5 min) to evaluate the perspective of implementing evidence-based practice. The Thresholds Supported Employment Leadership team will complete this brief survey prior to conducting the RCT.

**E. 2. Level 2.** The second level for the process evaluation of VR will take place after approximately 30 VR trainees completed their work with VR and will include a series of 2-4 focus groups (consisting of 4-6 research participants per group) with existing research participants using VR. The groups will assess perceptions of initial VR implementation, with results guiding immediate modifications to VR delivery. The focus groups will be video-recorded and last approximately 60 minutes. Video-recording is required for participation in the focus groups. Each participant will be paid \$20 for their time. The focus groups will be led by research staff and conducted at Thresholds. The participation in focus groups is a one-time experience. See attached list of questions guiding the focus group.

In addition, Level 2 will consist of recruiting Team Leaders and Employment Specialists to complete the 26item Implementation Survey for Providers (<10 min).

**E. 2. Level 3.** The third level for the process evaluation of VR will take place after approximately 60 VR trainees completed their work with VR and will include conducting focus groups with Employment Specialists and Team Leaders involved with the study to complete 1-3 focus groups (consisting of 4-6 Thresholds Staff). The groups will target a discussion around client, service, and implementation outcomes. The focus groups will be video-recorded and last approximately 60 minutes. Video-recording is required for participation in the focus groups... The focus groups will be led by research staff and conducted at Thresholds. The participation in focus groups is a one-time experience. See attached list of questioning guiding the focus group.

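### The modified-delivery flag is a possible covariate with no model named; only IPS+VR clients can have it, so in a two-arm model the arm term loses its randomized meaning

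*Combined protocol and SAP*

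**What the plan says.** Section 4.0, E. 2 Level 2, schedules client focus groups that "will take place after approximately 30 VR trainees completed their work with VR", "with results guiding immediate modifications to VR delivery". The Aim 3 part of section 14.0 (Study Procedures, Measures, and Data Analysis) adds a second round from the staff focus groups, "with results guiding new modifications to VR delivery", and then states: "We will track which subjects receive a modified delivery of VR, to be evaluated as a possible covariate". It gives no model, coding or population for that covariate.

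Section 4.0, D. 5, records a separate change. Employment Specialists and Team Leaders first ran the VR sessions; then "Due to workload expectations and coordination barriers, this responsibility was moved to the Thresholds Research Team". The same section lets IPS Only clients use VR only "following the completion of their participation in the study (after their 9-month follow-up phone call").

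The arm comparisons are in section 14.0, Data Analysis Plan for Aims 1 & 2. That section commits to intent to treat. For H1, "we will use multiple logistic regression and a Wald Chi-square test of the coefficient to its standard error". Its covariate paragraph provides for adjustment where the groups are seen to differ, and its list includes booster sessions and the number of completed interviews. H3 gives completed training trials as an example covariate. Modified delivery is not listed.

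**The concern.** A covariate in a two-arm model should be something that a participant in either arm could have, and preferably something fixed before randomization. This flag is neither. It arises after randomization, and no control can have it. Within the VR arm, original and modified delivery together make up the arm indicator, so adding the flag does not adjust the arm effect but splits it in two.

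At stake is what the main result means. The reported arm term would describe a subset of the VR arm, defined by when its members were trained, against controls from the whole recruitment period. Precision would be lost even if the modifications did nothing. The question that the flag is meant to answer, whether modification changed the effect, would stay confounded with calendar time because the flag has no control-arm counterpart.

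**Working it through.** **Inputs.** From H1 in section 14.0: 80 per arm, 10% missing (80 × 0.9 = 72 per arm), two-sided level 0.0125 (critical z = 2.498), OR 3.2, employment 25% vs 53%. From section 4.0, E. 2: client focus groups after about 30 VR trainees, staff groups after about 60. As fractions of 80 these are 37.5% and 75%. Using them, with 50% between, as shares on the original delivery is an assumption: the documents date the focus groups, not the start of changed delivery.

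**The plan's own figure.** OR 3.2 from 25% gives odds of 0.3333 × 3.2 = 1.067, or 51.6%. A two-proportion test with 72 per arm has 79.3% power, against 80% stated, so the figure reproduces. The stated 53% corresponds to OR (0.53/0.47)/(0.25/0.75) = 3.38, log OR 1.219.

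**What the arm term estimates.** Fit logit P(job) = a + b·arm + c·modified, with modified = 0 for all controls:
- IPS Only: a
- VR, original delivery: a + b
- VR, modified delivery: a + b + c

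So b is the log odds for original-delivery VR minus the log odds for all IPS Only. With the flag reversed (1 = original), b becomes modified-delivery VR against IPS Only. Centring the flag on its overall mean leaves b unchanged. None of these is the randomized contrast. The same split occurs in the H3 Cox model, and in H2 and H4 wherever the flag can act on the change or on the T3 score.

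**Power if modification has no effect (53% under both deliveries).** SE = √[1/(72 × 0.25 × 0.75) + 1/(n × 0.53 × 0.47)], where n is the number of VR clients the arm term rests on. Power = Φ(1.219/SE − 2.498).

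| Model | n | SE | Wald power |
|---|---|---|---|
| Arm only | 72 | 0.360 | 81% |
| + flag, 37.5% original | 27 | 0.472 | 53% |
| + flag, 50% original | 36 | 0.431 | 63% |
| + flag, 75% original | 54 | 0.385 | 75% |

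These rows use 1 = modified. With reverse coding, n is 45, 36 or 18 and power is 70%, 63% or 40%. Simulation (3,000 trials per case, 1 = modified) gives 54%, 65% and 76% with the flag, and 84% to 85% without it.

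**If modification does change the effect (illustration).** Let 37.5% have the original delivery with 40% employed. To keep the arm average at 53%, the modified rate is (0.53 − 0.375 × 0.40)/0.625 = 60.8%.
- Arm only: OR 3.38.
- Flag coded 1 = modified: OR (0.40/0.60)/(0.25/0.75) = 2.00, SE 0.478, power 15%.
- Flag reversed: OR 4.65, SE 0.409, power 90%.

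The same data give an odds ratio well below or well above the randomized one, depending only on coding. The 40% and 60.8% rates have no source in the documents.

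**The case against.** The strongest reply is that the plan never says it will do this. The sentence sits in the process evaluation and says only that the flag is a possibility to be evaluated. The Aims 1 & 2 covariate list omits it, and so do the H1 to H4 model descriptions. Another use is available: the exploratory person-level analysis under H5 relates the number of VR trials to job tenure and social skills, with training characteristics among its covariates. An analysis confined to the VR arm would be harmless.

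This narrows the point but does not remove it. The other Aim 3 analyses described are qualitative coding and budget impact, neither of which uses a participant-level regression covariate. The regressions that compare arms are in Aims 1 and 2, and that section already admits post-randomization exposure variables. Entry into those models is therefore a natural reading, and no sentence excludes it.

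Three stronger readings are tempting but unsupported. A reader might infer that the headline result will rest on an abandoned form of delivery. The only replaced mode on record is the staffing hand-over in D. 5. The plan does not say that this counts as modified delivery, and the content of the focus-group changes is unknown. A reader might infer that the VR effect would be understated, but that needs 1 = modified, a better modified version, and the flag in the model. Finally, 53% power might be taken as the expected loss. It is the low end of the range under that coding. If the hand-over counts as a change, the original-delivery share is unknown. Section 4.0, F. 1, also gives another focus-group trigger (one third of trial participants having completed training), and section 3.0 gives 180 recruits where section 14.0 uses 160.

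**Conclusion.** The concern holds as a conditional one. The primary model as written is not wrong, but the plan leaves open a covariate that would change what that model estimates. That the arm term would then stop being the intent-to-treat effect follows from the algebra and from the control arm having no VR during the study. It does not depend on any assumed rate.

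The size does rest on assumptions. With no modification effect and 1 = modified, H1 Wald power falls from 81% to between 53% and 75% for original-delivery shares of 37.5% to 75%. Reverse coding over the same shares gives 70% down to 40%. If modification alters employment, the odds ratio moves as well. Neither its direction nor its amount can be predicted from the documents, because the coding, the shares and the version-specific rates are not given. This should be settled before the analysis is run.

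**What to change.** Replace the sentence on tracking modified delivery with: *Delivery version will not enter the H1-H4 arm comparisons. It will be examined only in secondary analyses, either within the IPS+VR arm or as an arm-by-period interaction with period assigned by randomization date in both arms.*

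Period defined this way is fixed at randomization and exists for controls too, so early trainees are compared with early controls and the randomized contrast is kept. It needs only the randomization dates and the date of each delivery change. The plan should also say whether the D. 5 hand-over counts as one.

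The cost is small: one sentence and no new participant assessments. There are two drawbacks. The interaction test will have low power, and randomization date will misclassify a few trainees randomized before a change but trained after it. Restricting the flag to the VR arm is simpler and also cures the defect, but leaves delivery version confounded with calendar time.
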